## 2.6 Sonendo System Technology: Previous Clinical Experience

Five clinical studies have used the Sonendo System Technology. The first two studies are closed. The CS-01 dose feasibility clinical study included twenty-nine (29) patients. The CS-02 system feasibility clinical study enrolled twenty (20) patients that were treated with the Sonendo System Technology prior to tooth extraction.

Three studies are currently enrolling patients. Clinical study CS-02.1 has enrolled twenty (20) patients that were treated with the Sonendo GentleWave System prior to tooth extraction. In the CS-03 PURE study, molar teeth treated with the Sonendo System are evaluated for long-term performance of the System. A total of hundred and twenty two (122) patients have been enrolled to date in this study.

A fifth clinical study is CS-05, which is a randomized extraction study that will compare cleaning results in teeth treated with Sonendo GentleWave System and in teeth treated with traditional RCT. A total of seven (7) patients have been enrolled to date in this study.

A total of 198 patients have been treated with the Sonendo System.

#### 3.0 STUDY PURPOSE AND OBJECTIVES

The purpose of this study is to assess healing rates and post-procedure pain following root canal therapy with the Sonendo GentleWave System as compared to a literature control.

#### **3.1** Primary Effectiveness Endpoints

Subject teeth in the Treatment Complete cohort that are healed or are healing at the twentyfour month Follow-up Visit.

Healed is defined by absence of a radiographic indication of apical periodontitis (PAI <3) and absence of clinical signs and symptoms.

Healing is defined by a reduction of radiolucency (if radiolucency is present at Baseline) and/or reduction of clinical signs and symptoms (if clinical signs and symptoms are present at Baseline)

Secondary analysis will be performed after all Treatment Complete subjects have completed the 12 month Follow-up Visit.

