## 2.3 Healing Rates for Traditional Root Canal Therapy

While the literature presents many different definitions of healing, any future endodontic clinical studies should utilize a healing endpoint based upon both clinical and radiographic findings. The radiographic finding should be based upon the periapical index score, with PAI 1 or 2 indicating success. Additionally, no clinical signs or symptoms should be present. Separating complete healing and incomplete healing will also more clearly present study results.

Success rates over time varied widely across the literature. Generally, most healing had occurred 1 year following root canal treatment, though healing was shown to take up to 4 years or more. Thus, success rates should also be presented at each time-point studied and not just a cumulative number over a range of follow-up periods. An approximate success rate for 1 year follow-up would be 68-70% while that success rate would increase to 80-85% after four years.

While effective chemomechanical canal preparation is extremely important, the literature indicated other factors significantly affected long-term prognosis for the patient. If a patient presented with apical periodontitis and had a periapical lesion, the long-term success was significantly lower. Thus, including a large number of patients with a pre-operative periapical radiolucency could result in lower long-term success rates. Effective obturation to within 2 mm within the radiographic apex and effective coronal restorations also improved long-term success. The number of roots treated and mid-treatment complications could also impact success rates. These facts highlight the importance of choosing the appropriate patient

population and standardizing the treatment regimen in clinical studies so that the variable being studied can be reliably assessed.

While a number of studies have been published regarding the healing and success rates following root canal treatment, the quality of this literature is generally less than other medical disciplines. A dearth of randomized, controlled trials exists in endodontic research, and a large number of retrospective studies are published. Finally, the lack of standardization of study design and clinical endpoints across studies makes the comparison of results between studies difficult at best. *(See Appendix I. Healing Literature Report)* 

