## 13.1 Sample Size

All patients will receive root canal therapy with the Sonendo GentleWave System and will be subsequently followed for 24 months post procedure. A sample size of 108 subjects, assuming a 20% lost to follow-up or Treatment Incomplete Cohort rate, will result in approximately 86 subjects who would be evaluable for the primary efficacy endpoint. A sample size of 86 evauable subjects provides approximately 90% power to detect a difference between a 85% response rate for subjects using the Sonendo GentleWave System against a null hypothesis of a 70% response rate based on data presented in literature for traditional root canal therapy, using a two-sided binomial test at the 5% level of significance.

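### The primary endpoint pools Healed with Healing and is tested against a 70% literature rate whose definition of success is not shown, and no Healed-only comparison is planned

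*Combined protocol and SAP*

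**What the plan says.** Section 3.1 and the synopsis count as successes: "Subject teeth in the Treatment Complete cohort that are healed or are healing" at the 24-month visit. The two components are defined in the same place:

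- Healed requires a PAI score below 3 together with no clinical signs or symptoms.
- For the second component the wording is: "Healing is defined by a reduction of radiolucency (if radiolucency is present at Baseline) and/or reduction of clinical signs and symptoms". The signs and symptoms carry the same baseline condition. No minimum reduction is given.

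Section 2.3, on what future endodontic studies should use, says: "The radiographic finding should be based upon the periapical index score, with PAI 1 or 2 indicating success". It adds that signs and symptoms should be absent, and then: "Separating complete healing and incomplete healing will also more clearly present study results". It also notes that definitions of healing differ across the literature, gives success rates of 68-70% at one year and 80-85% after four years, and refers to Appendix I (Healing Literature Report).

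Section 13.1 assumes 85% for the device and tests it "against a null hypothesis of a 70% response rate based on data presented in literature for traditional root canal therapy", with 86 evaluable subjects, a two-sided binomial test at 5% and about 90% power. Section 13.4 plans one 24-month proportion with an exact 95% confidence interval. It names the outcome only as healing and does not restate the test.

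**The concern.** In a single-arm study with a literature control, the comparison is valid only if success means the same thing on both sides. The criterion recommended in 2.3 is in substance this protocol's Healed. The primary endpoint is wider, and its extra category is permissive. Because of the and/or, a tooth whose symptoms have eased counts as Healing even if its lesion is unchanged or larger.

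If the 70% describes complete healing, partly improved teeth are added to the device's numerator and not to the comparator's. A device no better than traditional therapy on complete healing could then exceed 70%. A single pooled proportion, as in 13.4, would not let a reader see this.

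**Working it through.** **Inputs from section 13.1.** n = 86; null 70%; alternative 85%; two-sided binomial test at 5%; 20% loss.

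**Assumed inputs, not in the documents.** The true Healed rate h is set to 70%, meaning no benefit on complete healing. The share s of not-Healed teeth that would be classed as Healing at 24 months is shown from 0% to 50%.

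**Step 1: reproduce the plan's figures.** For X successes among 86, the upper tail at 70% is P(X ≥ 68) = 0.0396 and P(X ≥ 69) = 0.0223. The test therefore rejects upward at 69/86 = 80.2% or more. The lower limit of the exact 95% interval passes 70% at the same count (0.7025 at 69, 0.6895 at 68). Power is P(X ≥ 69 | 85%) = 0.914, which agrees with the stated figure of about 90%. For enrolment, 86 / 0.80 = 107.5, rounded up to 108. The sample-size arithmetic is sound.

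**Step 2: effect of pooling if the 70% is a complete-healing rate.** The pooled rate is p = h + (1 − h)s = 0.70 + 0.30s. The chance of declaring superiority is P(X ≥ 69 | 86, p).

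| Share s classed as Healing (assumed) | Pooled rate | Chance of declaring superiority |
|---|---|---|
| 0% | 70% | 2.2% |
| 10% | 73% | 7.9% |
| 20% | 76% | 21.6% |
| 30% | 79% | 45.1% |
| 40% | 82% | 72.1% |
| 50% | 85% | 91.4% |

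**Step 3: thresholds.** With h = 70%, about 26 of 86 teeth are not Healed (86 × 0.30 = 25.8).

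- To reach the rejection boundary: (0.8023 − 0.70) / 0.30 = 34%, about 9 of the 26.
- To reproduce the full 15-point gain: (0.85 − 0.70) / 0.30 = 50%, about 13 of the 26.

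**Step 4: sensitivity to h.** At h = 68%, the lower end of the one-year range in 2.3, the chances for the same six shares are 0.8%, 3.8%, 13%, 33%, 62% and 86%.

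**Step 5: the null restated on the pooled scale.** If the comparator also gains 0.30s, the null becomes 0.70 + 0.30s. Power at a true pooled rate of 85% with n = 86 is then:

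| s (assumed) | Null | Reject at or above | Power at 85% |
|---|---|---|---|
| 10% | 73% | 72 | 69.5% |
| 20% | 76% | 74 | 46.6% |
| 30% | 79% | 76 | 24.0% |
| 40% | 82% | 78 | 8.6% |
| 50% | 85% | 80 | 2.0% |

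The definition behind the null therefore governs both the error rate and the power.

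**The case against.** The strongest objection is that the mismatch is not established. A reader might infer from 2.3 that the 70% was measured as PAI 1 or 2 without signs or symptoms, so that the pooled endpoint is certainly being compared with a stricter one. The documents do not support that. Section 2.3 recommends the strict criterion for future studies, does not say the 68-70% was obtained that way, and states that published definitions vary. The basis may be given in Appendix I, whose content is not in the text available here. If the 70% already includes incomplete healing, the inflation shrinks or disappears. This objection stands, and it makes the point conditional.

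Second, the size depends on assumed inputs. Section 2.3 says most healing occurs within a year, so few teeth may still be only Healing at 24 months. At a 10% share the chance is 7.9%, not 91%. This also stands, although the and/or wording leaves room for larger shares.

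Third, the sentence on separating complete and incomplete healing concerns presentation and does not forbid a pooled primary endpoint. That is correct.

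Fourth, PAI by independent reviewers is a secondary endpoint, and section 13.0 leaves analysis details to the statistical analysis plan. This helps only in part. PAI is the radiographic half of Healed, and section 13 contains no analysis of the full definition.

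**Conclusion.** The point holds as a conditional gap in justification. The plan tests a healed-or-healing rate against 70% without showing that the 70% is on that basis, and it plans no Healed-only result, although its own literature section favours the stricter criterion and the separation.

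If the 70% reflects complete healing and the device gives no benefit on that outcome, the chance of declaring superiority rises from 2.2% to between 7.9% and 91% as the share classed as Healing goes from 10% to 50%. This rests on a true Healed rate of 70%, 86 evaluable teeth and assumed shares. It would be too strong to say that the looser definition will produce the whole hypothesised gain: that needs half of the not-Healed teeth to qualify, and no document gives such a figure. Nor do the documents show that a pooled primary endpoint is wrong in itself. This should be fixed, but it does not by itself invalidate the design.

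**What to change.** 1. In 13.1 and 13.4, state the definition of success behind the 70%, with the part of Appendix I it comes from, and use a null on the same definition as the primary endpoint. Name the endpoint in 13.4 exactly as in 3.1.
2. Whichever endpoint stays primary, prespecify Healed alone at 24 months with its exact 95% confidence interval against the literature benchmark for complete healing. Do not claim superiority in complete healing unless the lower limit exceeds that benchmark. If the 70% proves to be a pooled rate, a complete-healing rate has to be taken from the literature for this analysis.
3. Report Healed, Healing and Not healed at 6, 12, 18 and 24 months as mutually exclusive categories, with Healing meaning improved but not meeting Healed. As now worded, a tooth whose baseline symptoms resolve fully and whose PAI is below 3 meets both definitions.

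**Cost.** Healed alone and the table need wording only, because PAI and the clinical assessments are already scheduled at all four visits (section 8.0). The Healed rate cannot exceed the pooled rate, so its power is less favourable and should be stated: with n = 86 against 70%, it is 91% if Healed is 85%, 72% if 82% and 54% if 80%. If the null is raised to a pooled basis, power falls as in step 5 and the sample size needs another look. Replacing the primary endpoint with Healed alone is a possible but debatable further step. Enrolment was expected to begin in August 2014 and this revision is dated March 2015, so the change could fall after enrolment had begun. The fix above does not depend on it.

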#### **3.3 Secondary Endpoints**

The following outcomes will be assessed:

- 1. McGill Short Form Pain Questionnaire
- 2. Gracely Descriptor Differential Scale (DDS) 59
- 3. Patient Satisfaction Survey
- 4. AAE Case Difficulty Assessment
- 5. Soft Tissue Lesions
- 6. Swelling
- 7. Root Canal Therapy Retreatment
- 8. Treatment Time
- 9. Procedure Time
- 10. Periapical Index (PAI) analyzed utilizing radiographic analysis by independent reviewer
- 11. Cone Beam Computed Tomography (CBCT) Sub-Set Evaluation
- 12. Additional Radiographic Analysis may be completed

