# 7.16 Crown Placement

Subjects enrolled in the study should obtain a permanent crown per standard of care. It is recommended that crown placement should occur within six weeks of the root canal therapy procedure per standard of care. For the protocol, final crown placement date will be the date CRC obtains from the subject and/or GP and/or the Investigator.

Pain and tenderness to percussion, palpation, ill-fitting margins, open margins, high occlusal contact points with the opposing teeth or any other restoration related issues after crown placement experienced by the patient or reported by the PI and/or SD and/or Crown Placement dentist, will not be considered an adverse event but will be documented.

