# 7.17.2 Follow-Up Visit Evaluations and Assessments

These study follow-up visits will occur at the clinical site and the following assessments will occur according to standard of care at each visit:

- 1. Medication Regime: Only prescribed herbal or over the counter systemic antibiotics, analgesics, and anti-inflammatory medications taken during the duration of the study (24 months post procedure) and the prior three months will be documented for this study.
- 2. McGill Short Form Pain Questionnaire: The McGill Pain Questionnaire (MPQ) is one of the most widely used tests for the measurement of pain. It provides information on sensory, affective, and evaluative dimensions of pain experience and is capable of discriminating among different pain problems.
- 3. Diagnostic Radiographic Analysis: Periapical (PA) Parallel Radiograph, showing the periapical region surrounding the subject tooth should be collected for each visit. Additional radiographs completed as necessary by the PI will be collected for the study.
- 4. Periapical Index (PAI) Score analyzed by independent reviewer

Up to three (3) independent reviews will be provided radiographs in order to complete the PAI scoring. Independent reviewers will be blinded to the site, subject, and visit when completing the PAI score. This is being done to eliminate bias.

- Score of 1: Normal
- Score of 2: Small changes in bone structure
- Score of 3: Changes in bone structure with some mineral loss (bone loss)
- Score of 4: Periodontitis with well-defined radiolucent area (apical periodontitis)
- Score of 5: Severe Periodontitis with exacerbating features (apical periodontitis)

Note: A Protocol Deviation CRF will not be completed if PAI score was not completed by independent reviewer for a particular visit. In addition there is no defined study window for completion of PAI scoring by independent reviewer.

- 5. Dental Cone Beam Computed Tomography (CBCT) at 12 and 24 months and additional as required by the PI.
- 6. Intra-Oral Examination including, but not limited to:
  - a. Tooth Number: Based on the Universal Tooth Numbering System (1-32)
  - b. Subject Tooth Assessments including:

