- Acute Apical Abscess: An inflammatory reaction to pulpal infection and necrosis characterized by rapid onset, spontaneous pain, tenderness of the tooth to pressure, pus formation, and swelling of associated tissues.
- Chronic Apical Abscess: An inflammatory reaction to pulpal infection and necrosis characterized by gradual onset, little or no discomfort, and the intermittent discharge of pus through an associated sinus tract.
- Condensing Osteitis: Diffuse radiopaque lesion representing a localized bony reaction to a low-grade inflammatory stimulus, usually seen at apex of tooth
- 8. Adverse Events (see Section 10.0 Adverse Event).

After assessments are completed, the patient may be prescribed medication(s) for pain management according to standard of care procedures. If analgesic medications need to be provided to the patient in order to complete one or more of the assessments, the assessments that require a pain response (i.e. cold test, percussion and palpation) should be completed prior to providing this medication.

All redacted source documentation with PI signature should be provided to the Sponsor for filing after each study visit. If changes are made to the source documents after PI signature, the updated source documents should be provided to the Sponsor for filing.

In addition, the clinical site designee will report all significant findings at Follow-Up Visits to the Sponsor either via email or by sending redacted source documentation.

Subjects should be evaluated to determine if the subject tooth remains functional. If the subject tooth is or still requires healing, the subject should be evaluated closely. If the subject has clinical symptoms or signs after the twelve month follow-up, the PI should follow standard endodontic care, as applicable. All such care should be documented accordingly for the study.

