#### **8.0 SCHEDULE OF VISITS**

Description	Screening	Baseline	Procedure  (+7 ds)	Post- Operative	1 day	2 days	3 days	7 days	14 days	6 mo. (± 14ds)	12 mo. (± 30ds)	18 mo. (± 30ds)	24 mo.² (± 45ds)	Unsched uled Visits
Screening Form by Screening Dentist or Pl	x													VISIUS
Images of Smile & Oclussal Surface	х													
X-Rays (Periapical) 	x	x	x	х						х	х	х	х	As needed
Medical and Dental History	х	x								х	x	х	х	As needed
Medication Regimen Review	x	x								х	х	х	х	As needed
Informed Consent		x								As needed	As needed	As needed	As needed	As needed
СВСТ		X, if applicable		X, if applicable							X, if applicable		X, if applicab le	As needed
McGill Short Form		х			x	х	х	x	х	х	x	х	х	As needed
Gracely DDS		x		x	x									
Periapical Index Score		x								х	х	х	х	As needed
General Dental and Endodontic Assessments		x								х	x	х	x	As needed
Sonendo GentleWave Treatment			x											
Root Canal Therapy			х											
Intra Assessments and Evaluations			x											
Post Operative Assessments and Evaluations				х										
Patient Satisfaction Survey				х										
AAE Case Difficulty Assessment				x										
Adverse Event Assessment			x	x						х	x	х	х	As needed

- 1. The procedure must be completed within seven days (7) of the baseline visit. For any treatment not completed within seven days of the baseline, the baseline assessments must be completed again within the time frame indicated. In addition, if a subject must return to the clinical site for completion of a procedure, as indicated in *Section 7.9 Second Procedure* Visit, this must also occur within seven days of the baseline.
- 2. Subjects may be asked to have a follow-up visit every year after the twenty-four (24) month visit for up to ten (10) years.
- 3. Only PA Parallel radiographs will be obtained.

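### The healing limb of the primary endpoint has no bar on worsening, so a tooth symptomatic at Baseline without a radiolucency can gain a new lesion, hurt less, and count as a primary success

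*Combined protocol and SAP*

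**What the plan says.** Section 3.1, repeated in the Synopsis, makes the primary success a Treatment Complete tooth that is either *healed* or *healing* at month 24. *Healed* is an absolute standard: PAI below 3 and no clinical signs or symptoms. *Healing* is relative to Baseline: "Healing is defined by a reduction of radiolucency (if radiolucency is present at Baseline) and/or reduction of clinical signs and symptoms", with the second part also conditional on presence at Baseline. Neither place adds a condition about new or worse findings. Section 13.4 reports one proportion with an exact 95% confidence interval and adds nothing to the definition.

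Section 2.3 sets out what an endodontic endpoint should look like: clinical and radiographic findings together, PAI 1 or 2 as success, and no signs or symptoms. It also advises that "Separating complete healing and incomplete healing will also more clearly present study results". For the literature behind the benchmark it refers the reader onward ("See Appendix I. Healing Literature Report").

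On retreatment, Section 3.3 lists "Root Canal Therapy Retreatment" among the secondary endpoints. Section 7.17.2 says "If the subject has clinical symptoms or signs after the twelve month follow-up, the PI should follow standard endodontic care, as applicable" and has that care documented. It does not name retreatment or say how such a tooth then counts. Sections 9.7, 13.2, 13.4 and 13.7 give no class for it. Section 13.0 leaves details of analysis methods to a statistical analysis plan.

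**The concern.** A primary success should not include a tooth whose periapical state is worse than when it was treated. The *healing* limb asks only whether something present at Baseline has lessened. It never asks whether something else has appeared or grown. Symptoms can ease while a lesion develops, so the two components can move in opposite directions, and the definition then credits the tooth.

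What is at stake is the meaning of the reported success rate, and how that rate compares with the 70% null in Section 13.1. Any worsened tooth that is credited moves the count upwards.

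Retreatment is a smaller, separate gap. It is a failure-type event with no stated class in the primary analysis.

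**Working it through.** **1. The definition applied to two teeth**

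| Tooth | Healed? | Healing, and/or read as *and* | Healing, and/or read as *or* |
|---|---|---|---|
| A: symptoms, no radiolucency at Baseline; PAI 3 or more and fewer symptoms at month 24 | No (PAI not below 3) | Yes: the radiolucency condition does not apply, the symptom condition is met | Yes |
| B: radiolucency and symptoms at Baseline; larger lesion (PAI 3 or more) and fewer symptoms at month 24 | No | No | Yes |

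Tooth A succeeds on both readings, because the radiolucency condition binds only when a radiolucency was there at Baseline. Tooth B succeeds on the *or* reading only.

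Teeth like A can enrol. Section 5.1 asks only that the tooth be a first or second molar indicated for root canal therapy. The diagnostic categories in Section 7.4.4 include symptomatic irreversible pulpitis, and symptomatic apical periodontitis with or without an apical radiolucency.

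**2. The plan's own figure**

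Inputs from Section 13.1: 86 evaluable, null 70%, expected 85%, two-sided 5% binomial test, 20% loss, 108 enrolled.

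- Enrolment: 86 / 0.80 = 107.5, rounded up to 108, as stated.
- Cut-off: the smallest x with P(X ≥ x | 86, 0.70) ≤ 0.025 is 69, with upper-tail probability 0.0223.
- Power: P(X ≥ 69 | 86, 0.85) = 0.914, which agrees with the stated figure of about 90%.
- Exact 95% interval, as in Section 13.4: 69/86 = 80.2% (70.25% to 88.04%), which lies above 70%; 68/86 = 79.1% (68.95% to 87.10%), which does not.

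The sample size is sound on its own inputs and is not in dispute.

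**3. Illustration of the effect**

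Assumptions, not document figures: X is the number of teeth that are healed, or healing without worsening; X ~ Bin(86, 0.70); k worsened teeth among the rest are credited as healing. The count reaches the cut-off if X + k ≥ 69.

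| k (assumed) | Event | Probability |
|---|---|---|
| 0 | X ≥ 69 | 2.2% |
| 1 | X ≥ 68 | 4.0% |
| 2 | X ≥ 67 | 6.6% |
| 3 | X ≥ 66 | 10.4% |

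**4. Illustration of the cost in power**

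If the planned 85% had counted on average k worsened teeth, the rate without them is 0.85 − k/86. Power at the same cut-off is P(X ≥ 69 | 86, 0.85 − k/86).

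| k (assumed) | Rate | Power |
|---|---|---|
| 0 | 85.0% | 91% |
| 1 | 83.8% | 85% |
| 2 | 82.7% | 77% |
| 3 | 81.5% | 68% |

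**The case against.** *The benchmark may be equally lenient.* The literature report behind the 70% is not in the text available. If the literature counted such teeth as successes, crediting them here causes no excess error, and a stricter definition would tilt the comparison against the device. This stands. A reader might infer from step 3 that the trial's false-positive rate is inflated, but the documents do not show that the null excludes worsened teeth.

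*The frequency is unknown.* This also stands. The values of k are assumed, and the cut-off of 69 is derived from Section 13.1, since Section 13.4 promises only a proportion and an interval. At the planned rate the expected count is 0.85 × 86 = 73.1, and a result of exactly 69 has a probability of only about 5%.

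*New lesions would be seen anyway.* Blinded PAI is a secondary endpoint, and a periradicular diagnosis is made at each follow-up. That helps a careful reader, but nothing lets either finding override the symptom route to primary success. Section 7.17.2 also sets no window for PAI scoring and says "A Protocol Deviation CRF will not be completed if PAI score was not completed by independent reviewer for a particular visit".

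*Healing should mean improvement in every component present at Baseline.* A reader might draw this from Section 2.3, but it goes beyond the defect. It would turn and/or into and. A tooth whose lesion shrank while its symptoms stayed the same, with nothing worse, would then fail; on the *or* reading it now succeeds. That is a different, stricter endpoint.

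*Retreated teeth count as successes, or will be classed after the data are seen.* Neither is shown. No rule makes a retreated tooth a success, and one may exist in the statistical analysis plan that Section 13.0 mentions. What stands is that the text available gives no class.

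**Conclusion.** The point holds as a gap in a stated rule. As Section 3.1 and the Synopsis are written, a tooth with signs or symptoms but no radiolucency at Baseline that has PAI 3 or more and fewer symptoms at month 24 is a primary success on either reading of and/or. A tooth whose Baseline lesion grows while symptoms ease is one on the *or* reading only. No other section overrides this.

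The size cannot be estimated from the documents. The rise from 2.2% to as much as 10.4% rests on three assumptions: a 70% rate without worsened teeth, one to three such teeth credited, and a cut-off of 69 out of 86. It describes a false-positive rate only if the 70% null excludes such teeth. No mismatch with the benchmark is claimed. Confidence is high on the wording of the definition and much lower on the practical effect. The class of a retreated tooth is a minor, unspecified case.

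**What to change.** In the Synopsis and Section 3.1, keep success as healed or healing and keep the existing and/or wording. Add that a tooth is not *healing* if at month 24 it has either:

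- a new or enlarged radiolucency, meaning blinded PAI that has gone from below 3 to 3 or more, or that is above its Baseline value where Baseline PAI was 3 or more; or
- a new or worse endodontic clinical sign or symptom.

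Findings attributed to the restoration, which Section 7.16 already sets apart ("any other restoration related issues after crown placement"), are documented but do not count as worsening. Do not add a requirement that every component present at Baseline be reduced.

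Use the same definition in Section 13.4, and report the healed and healing proportions separately, each with an exact 95% interval, as Section 2.3 advises. As a minor addition, state in advance how a tooth retreated before month 24 is classed, for example as not healed, or point to the rule if the statistical analysis plan already has one.

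The cost is mainly wording and two further proportions. PAI and the "General Dental and Endodontic Assessments" are already scheduled at Baseline and month 24 in Section 8.0, so no new assessment is needed, but month-24 blinded PAI scoring must actually be completed. The reported rate may be slightly lower; it is unchanged if no worsened or retreated teeth occur. If the planning rate of 85% had included worsened teeth, the loss of power is as shown in step 4 of the working.
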